## **8.1 Assessment and Reporting of Adverse Events**

To monitor subject safety throughout this study, any procedure or device related adverse events will be recorded. Information on all adverse events will be maintained by event type. The investigator will complete an Adverse Event form if any adverse event is reported or observed for a subject during this study, even if the event was acknowledged as a risk factor in the Informed Consent form.

Adverse device effects refer to any undesirable clinical or medical occurrence associated with use of the device or participation in the study. Any/all adverse device effects are to be recorded via the Adverse Event form. Adverse device effects will be reported if observed, even if they were acknowledged as risk factors in the Informed Consent form.

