## 7. Investigational Procedures

### 7.1 Design Overview

The Implantation with the Cochlear Nucleus® CI532 Implant - Early Experience Study will be conducted as a multi-center, prospective, single-arm clinical study, evaluating the safety and functionality of the Cochlear Nucleus CI532 cochlear implant in up to 50 subjects who meet current cochlear implant indications. A single-subject repeated-measures analysis will be employed whereby subjects will act as their own control. A single-subject research design is appropriate since it accommodates the heterogeneity that characterizes hearing-impaired populations. Blinding procedures are not appropriate for this trial design, as it is not possible to conceal the presence, or absence, of a cochlear implant from device recipients and/or clinical investigators.

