## 7.4 Intraoperative Procedures

### 7.4.1 Visit 2

There are no modifications to the standard surgical procedure for this study.

All surgeons will be required to complete a surgical questionnaire for each implanted subject. Intraoperative measures (impedance and NRT) are optional.

Additionally, intraoperative imaging (plain film x-ray) is recommended but not required, consistent with the Cochlear Nucleus CI532 Surgeons Guide.

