## 7.5 Postoperative Procedures

### 7.5.1 Visit 3

At the initial activation appointment, the following procedures will be completed:

---

CONFIDENTIAL

March 31, 2016

CAM-CL-027\_PRT

Rev. 1

Page 12 of 21

Cochlear

- 1) Tympanometry, both ears.
- 2) Frequency-specific thresholds at standard audiometric frequencies for both ears.
  - a) Air conduction: 125, 250, 500, 750, 1000, 2000, 3000, 4000, and 8000 Hz
  - b) Bone conduction: 250, 500, 1000, 2000, 3000 and 4000 Hz
- 3) The initial activation will be performed according to standard clinical procedures using Custom Sound and the default programming settings for the Nucleus 6 sound processor.
  - a) Impedances and NRT are to be measured.
  - b) An anonymous .cdx file will be provided to the study sponsor.
- 4) Audiologist Questionnaire will be completed for each subject.

#### 7.5.2 Visit 4

At 3 months postactivation, the following procedures will be completed:

- 1) Tympanometry, both ears.
- 2) Frequency-specific thresholds at standard audiometric frequencies for both ears.
  - a) Air conduction: 125, 250, 500, 750, 1000, 2000, 3000, 4000, and 8000 Hz
  - b) Bone conduction: 250, 500, 1000, 2000, 3000 and 4000 Hz
- 3) Aided speech recognition in quiet: AzBio sentences (Spahr et al., 2012) presented at 60 dBA in the sound field for the unilateral listening ear.
  - a) Only to be collected on subjects aged 12 years and older.
- 4) Aided speech recognition in noise: AzBio sentences (Spahr et al., 2012) using speech weighted noise presented at 65 dBA with a +5 dB signal to noise ratio spatially separated, speech 0 degrees azimuth and noise 90 degrees towards the implanted ear for the unilateral listening ear.
  - a) Only to be collected on subjects aged 12 years and older.
- 5) Mapping will be performed according to standard clinical procedures using Custom Sound and the default programming settings for the Nucleus 6 sound processor.
  - a) Impedances and NRT are to be measured.
  - b) An anonymous .cdx file will be provided to the study sponsor.

---

CONFIDENTIAL

March 31, 2016

CAM-CL-027\_PRT

Rev. 1

Page 13 of 21

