## 7.6 Summary of Data Collection Visits

	Visit 1	Visit 2	Visit 3	Visit 4
Test	Baseline	Surgery	Initial Activation	3 Mos Post Activation
Informed Consent	X			
Tympanometry	X		X	X
Audiometric	X		X	X
AzBio Quiet	X*			X*
AzBio Noise	X*			X*
Surgical Questionnaire		X		
Intraoperative Testing		X (optional)		
Imaging		X (optional)		
Audiological Questionnaire			X	
Device Programming (.cdx)			X	X

\*Note for subjects aged 12 years and older.

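### Safety is a stated aim, but no visit is specified to ask about adverse events, so adverse-event counts risk being too low

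*Protocol*

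**What the plan says.** Protocol 7.1 describes a single-arm study "evaluating the safety and functionality of the Cochlear Nucleus CI532 cochlear implant in up to 50 subjects". Section 10.1 makes everyone who consents the population for evaluating safety.

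Section 8.1 opens with a general duty: "To monitor subject safety throughout this study, any procedure or device related adverse events will be recorded". The operative instruction follows: "The investigator will complete an Adverse Event form if any adverse event is reported or observed for a subject during this study". For adverse device effects it says: "Adverse device effects will be reported if observed, even if they were acknowledged as risk factors in the Informed Consent form". None of these sentences states a method of elicitation.

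The visit content is in 7.3 to 7.5 and is tabulated in 7.6 ("Summary of Data Collection Visits"). The table covers consent, tympanometry, audiometry, AzBio in quiet and in noise, a surgical questionnaire, optional intraoperative testing and imaging, an audiological questionnaire, and device programming. The list for the last visit is introduced by "At 3 months postactivation, the following procedures will be completed" and has five items, none of them an adverse-event enquiry.

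Two forms are required for each subject. For Visit 2, 7.4.1 states: "All surgeons will be required to complete a surgical questionnaire for each implanted subject". At Visit 3, 7.5.1 requires an audiologist questionnaire. The protocol does not describe the content of either. The SAP does not mention adverse events.

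**The concern.** In a single-arm study the safety result is an absolute rate: subjects with a recorded event, divided by subjects in the safety population. No comparator arm shares the same under-capture. A missed event can only lower that rate.

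If nobody is required to ask, what gets recorded depends on what a subject chooses to mention, what an investigator notices, and how each site habitually takes a history. Two things follow. Milder events, or events that have resolved by the next visit, may never reach a form. Rates may also differ between sites because practice differs. A blank record would then not show whether the subject had no event or was not asked.

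The interval from surgery to activation is the most exposed. The schedule has no visit between them, and the length of that interval is not stated.

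**Working it through.** The documents state no adverse-event rate, safety threshold or safety sample size. The sample size in 10.2 concerns AzBio sentence scores only. There is therefore no plan figure to reproduce, and the check is mainly of the text.

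**Step 1: where could an enquiry be specified?**

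| Visit | Section | Adverse-event enquiry listed? | Other routes to detection |
|---|---|---|---|
| 1, baseline | 7.3.1 | No | Before surgery |
| 2, surgery | 7.4.1 | No | Surgical questionnaire, content not given |
| 3, activation | 7.5.1 | No | Audiologist questionnaire, content not given; tympanometry, audiometry, impedances and NRT |
| 4, 3 months | 7.5.2 | No | Tympanometry, audiometry, impedances and NRT; no questionnaire |

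Even if both questionnaires ask about complications, they stop at Visit 3. Activation to 3 months, the whole period of device use under study, has no specified enquiry. The same sections list every audiometric frequency and the speech presentation levels, so the protocol does spell out visit content where it wants something collected.

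**Step 2: what is recorded once an event is known?** Section 8 defines an adverse event by its association with the device, the procedure or taking part. The opening of 8.1 likewise refers to events related to procedure or device. For non-serious events, a judgement of association therefore comes into the definition before recording. The serious-event definition in section 8 carries no such condition.

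**Step 3: what happens at discontinuation?** Section 9.2 requires a withdrawal form giving the reason, and an adverse event is one listed reason. That captures an event that caused withdrawal, but not other events before it. Subjects who receive an alternative device at surgery are discontinued under 9.2 yet remain in the safety population of 10.1.

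**Step 4: illustration of sensitivity.** Both inputs are assumptions: a true per-subject rate p of 5 to 20%, and a captured share s of 50 to 100%. I take n = 50, the maximum number implanted; the number consented is not given. Expected recorded subjects = n × p × s. Chance of recording at least one = 1 − (1 − p·s)^n.

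| p | s = 100% | s = 75% | s = 50% |
|---|---|---|---|
| 5% | 2.5; 0.92 | 1.9; 0.85 | 1.25; 0.72 |
| 10% | 5.0; 0.995 | 3.75; 0.98 | 2.5; 0.92 |
| 20% | 10; 1.00 | 7.5; 1.00 | 5; 0.995 |

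Example: p = 5%, s = 50% gives 50 × 0.05 × 0.5 = 1.25 and 1 − 0.975^50 = 0.72.

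If no event is recorded in 50 subjects, the one-sided 95% upper bound on the recorded rate is 1 − 0.05^(1/50) = 5.8%. This is also a bound on the true rate only if ascertainment is complete. With captured share s the bound on the true rate is 5.8%/s: 5.8/0.75 = 7.7%, or 5.8/0.5 = 11.6%.

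The table shows direction and proportionality. It does not estimate this study's shortfall.

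**The case against.** The strongest reply is that the protocol is silent on enquiry, and silence does not show that nobody asks. An event that is reported may well be an answer to a question. The scheduled tests at Visits 3 and 4 let investigators find some problems directly. The two questionnaires and the CRFs are not in the documents and may already include the question. All of this stands, and it rules out three stronger readings that a reader might infer.

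- *Events are recorded only if volunteered.* The text of 8.1 does not say so.
- *No visit asks, so the safety result is biased.* The documents show only that no visit is specified to ask. Under-counting is a risk, not an established fact.
- *Only events already judged related are recorded.* Section 8.1 does not say only. It also requires a form for any adverse event, and the section 8 definition extends to events associated with study participation. What can be said is that the definition for non-serious events rests on association.

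It is also fair that the consequence is limited. Safety is not among the objectives or endpoints in section 2, there is no safety hypothesis, and the device is commercially available.

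The reply does not cover Visit 4, where no questionnaire is scheduled. Nor does it offer a common method across sites for a study that says it evaluates safety.

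**Conclusion.** The point holds in limited form. The protocol declares a safety evaluation and a safety population but specifies no adverse-event enquiry at any visit, and from activation to 3 months not even an undescribed questionnaire could fill the gap. Followed as written, counts risk being too low and may vary between sites.

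The size cannot be derived. Under incomplete capture the expected count falls in proportion to the share captured, but neither that share nor the true rate is in the documents. The conclusion assumes that the unseen questionnaires and CRFs do not already contain a standard question covering every interval. If they do, what remains is that 8.1 and 7.6 should say so. The AzBio comparisons are not affected. The change should be made because it alters which data are collected and costs little.

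**What to change.** 1. Add an *Adverse event review* row to 7.6 at Visits 3 and 4, and a matching line to 7.5.1 and 7.5.2: one standard, open, non-leading question about any event since the last visit, with a yes/no field. At Visit 3 this covers surgery to activation. Visit 2 is the operation itself and could not recover those events.
2. Ask the same question at any withdrawal contact under 9.2, including for subjects discontinued after receiving an alternative device.
3. State in 8.1 that events reported on enquiry are recorded, with relationship to device or procedure entered as a field on the form. Align the section 8 definition with this; changing 8.1 alone would leave the two in conflict.
4. If the questionnaires or CRFs already ask, say so in 8.1 and add the question at Visit 4.
5. Where data have already been collected, report how events were elicited, so that a zero or low count can be read correctly.

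Cost: one question and one field at two existing visits and at withdrawal contacts, a few more forms, and a slightly higher reported event rate.

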## **8.2 Unanticipated Adverse Device Effects**

Unanticipated adverse device effects refer to any event not identified above that represents a “serious adverse effect on health or safety or any life-threatening problem or death caused by, or associated with, a device if that effect, problem or death was not previously identified in nature, severity, or degree of incidence in the investigational plan or application, or any other unanticipated serious problem associated with a device that relates to the rights, safety, or welfare of subjects.” [FDA 21 CFR 812.3(s)]

Investigators are to inform their respective Institutional Review Boards (IRBs) and Cochlear Americas immediately if an unanticipated adverse device effect is suspected (no more than 10 working days after the investigator learns of the effect). If the case is determined to be an unanticipated adverse device effect, the investigator will fill out an “Unanticipated Adverse Device Effect Form.” Cochlear Americas will report the results of an evaluation of the unanticipated adverse device effect to all reviewing IRBs and investigators within 10 working days after first receiving notice of the event.

---

CONFIDENTIAL

March 31, 2016

CAM-CL-027\_PRT

Rev. 1

Page 15 of 21

Cochlear

## **9. Study Completion**

### **9.1 Completed Subjects**

Once the 3 month postactivation visit is completed, the subject will be deemed complete. Subjects will continue to receive standard clinical follow-up care at their cochlear implant facility after the study.

### **9.2 Discontinued Subjects**

Any subject may voluntarily discontinue the study at any time without prejudice. The Investigator may discontinue a subject from the study at any time if (s)he considers that remaining in the study compromises the subject's health or the subject is not sufficiently cooperative. In either event, reason(s) for discontinuation should be recorded on a study withdrawal form, provided as part of the CRFs for the study. Possible reasons for study discontinuation include the following:

- AE necessitating discontinuation from the study
- The subject is lost to follow-up
- Voluntary decision to withdraw consent made by the subject
- Investigator decision
- Other reason

In case of a subject lost-to-follow-up, the Investigator must attempt to contact the subject (or relative/family contact) by phone, email or letter at least three times. If attempts are unsuccessful, the 'subject withdrawal' form is to be completed in the study file and reported, as appropriate, in required reports to the Sponsor and IRB.

During surgery, an alternative device (e.g., CI522 or CI512) may be implanted in subjects where there are difficulties with the CI532. These subjects will be discontinued from the study.

Subjects who withdraw or are discontinued prior to the completion of the 3 month visit will receive compensation of \$12.50/ hour for the cumulative period of time spent on study procedures.

### **9.3 Premature Study Termination**

The Sponsor may terminate the study early in the case of major non-adherence to the protocol, or if it is anticipated that recruitment will not be met for the required number of subjects to complete the study objectives. In the event of

---

CONFIDENTIAL

March 31, 2016

CAM-CL-027\_PRT

Rev. 1

Page 16 of 21

premature study termination, the subjects who are already enrolled will be sponsored through study completion.

## **10. Data Analysis**

### **10.1 Statistical Analysis**

All subjects who are consented into the clinical study will constitute the intention-to-treat (ITT) population for the purposes of safety evaluation. Only subjects implanted with the CI532 and completed per the protocol will be considered as the completed cases (CC) population and per protocol (PP).

Demographic and outcomes data will be tabulated individually along with group summary descriptive statistics. Speech perception scores will be presented for each study evaluation, pre- and postoperatively, so that postoperative progress can be evaluated over time.

Performance with the Nucleus CI532 will be determined by a comparison of preoperative, best aided, ear to be implanted vs. 3 months postactivation outcome measures. The speech perception measures chosen for this purpose are the AzBio sentences in both quiet and noise in the unilateral listening condition.

The primary study endpoints will be statistically significant differences between the mean, preoperative speech perception scores and postoperative scores for the activated, CI532 cochlear implant subjects who completed speech perception testing. Mean scores as measured by AzBio sentences in quiet and noise will be compared. The null hypothesis to be tested is that there is no difference for the subjects between their pre- vs. postoperative speech performance

Individual scores obtained at 3 months will be compared with those obtained, on the same measures preoperatively, based on the binomial model where appropriate (see Thornton and Raffin, 1978; Boothroyd and Nittrouer, 1988). Although the binomial model is the more appropriate statistical model for analysis of single-subject experimental data, conventional group-based statistics will also be applied to the pooled results. For all of the speech perception measures, nonparametric procedures (e.g., a Signed-Ranks test) will be conducted in order to further confirm the results of the single-subject analyses. These tests will be two-tailed and applied using an alpha level of 0.05.

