### **6.2 Exclusion Criteria**

- Previous cochlear implantation in the ear to be implanted
- Pre-linguistically deafened (onset of hearing loss at less than two years of age)
- Women who may be pregnant at the time of cochlear implant surgery
- Ossification or any other cochlear anomaly that might prevent complete insertion of the electrode array
- Diagnosis of retro-cochlear pathology
- Diagnosis of auditory neuropathy
- Unrealistic expectations on the part of the subject regarding the possible benefits, risks, and limitations that are inherent to the surgical procedure and use of the prosthetic device
- Unwillingness or inability to comply with all investigational requirements
- Additional cognitive handicaps that would prevent participation on all study requirements

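### No count of attempted CI532 implantations converted to another device is planned, and the all-consented safety denominator can make procedure- and device-related event rates read low

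*Protocol*

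**What the plan says.** **Conversion.** Protocol 9.2 provides that during surgery "an alternative device (e.g., CI522 or CI512) may be implanted in subjects where there are difficulties with the CI532". It continues: "These subjects will be discontinued from the study". Protocol 6.2 has already excluded "Ossification or any other cochlear anomaly that might prevent complete insertion of the electrode array", so conversions would arise among patients who passed that screen.

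**Primary comparison.** Protocol 10.1 compares mean pre- and postoperative AzBio scores "for the activated, CI532 cochlear implant subjects who completed speech perception testing", and the SAP repeats the restriction in the same words. Protocol 10.1 also defines the completed-cases and per-protocol sets as CI532 subjects who finished the study.

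**Planned tabulation.** Both documents plan individual and summary tables of demographic and outcome data. Neither mentions disposition, attempted implantations or conversions.

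**Safety.** Protocol 10.1 states: "All subjects who are consented into the clinical study will constitute the intention-to-treat (ITT) population for the purposes of safety evaluation". Protocol 16 places consent before any study examination. Protocol 8.1 says that "any procedure or device related adverse events will be recorded", with a form to be completed "if any adverse event is reported or observed for a subject during this study". The SAP does not discuss safety.

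**The concern.** Protocol 7.1 describes a single-arm study evaluating the safety and functionality of the CI532. A surgeon's decision to implant something else because of difficulties with the study device bears on both, yet those subjects leave the performance result and no planned output counts them.

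Readers could not recover the number from the count of subjects with scores. That count also falls through loss to follow-up and withdrawal, and because sentence testing is limited to subjects aged 12 or older (7.2.1) while 10.2 provides for enrolling younger ones. Without a separate conversion count, nobody can judge how selected the completers are.

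The safety set has a different problem. Someone who consents but never reaches surgery cannot have a procedure- or device-related event. Including such subjects in a denominator can only lower the rate.

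**Working it through.** The plan gives no figure for conversions or for consented subjects not operated on, so there is no stated result to reproduce. The only planning number used is the ceiling of 50 implanted subjects (Protocol 1 and 10.2). All event and conversion counts below are assumptions chosen to show scale.

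**Step 1: follow a converted subject through the plan.**
- 9.2: another device is implanted and the subject is discontinued, so no 3-month study score is due.
- 10.1 and SAP: not an activated CI532 subject with completed testing, so not in the primary comparison and not in the completed-cases or per-protocol set.
- 10.1: consented, so still in the safety population.
- Possible records of the conversion: the surgical questionnaire required for each implanted subject (7.4.1), the withdrawal form (9.2) and, if an event occurred, the Adverse Event form (8.1).
- Planned summary of those records as conversions: none in 10.1 or the SAP.

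**Step 2: what a reported conversion proportion would show.** For x conversions in n attempts, the exact (Clopper-Pearson) 95% limits are the 0.025 quantile of Beta(x, n − x + 1) and the 0.975 quantile of Beta(x + 1, n − x). With n = 50:

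| Conversions | Proportion | Exact 95% CI |
|---|---|---|
| 0 | 0% | 0% to 7.1% |
| 1 | 2.0% | 0.05% to 10.6% |
| 3 | 6.0% | 1.3% to 16.5% |
| 5 | 10.0% | 3.3% to 21.8% |

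For x = 0 the upper limit is 1 − 0.025^(1/50) = 0.071. Even no conversions at full enrolment would leave a rate of about 7% possible, so the interval belongs beside the count.

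**Step 3: the safety denominator.** Let e be the number of subjects with an event, C the number consented and O the number operated on. The rate per consented subject is e/C and per operated subject e/O, so the first is O/C times the second. Take C = 50 and e = 3, giving 3/50 = 6.0% per consented subject:

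| Not operated on | O | Factor O/C | Rate per operated subject |
|---|---|---|---|
| 0 | 50 | 1.00 | 3/50 = 6.0% |
| 1 | 49 | 0.98 | 3/49 = 6.1% |
| 2 | 48 | 0.96 | 3/48 = 6.3% |
| 5 | 45 | 0.90 | 3/45 = 6.7% |
| 10 | 40 | 0.80 | 3/40 = 7.5% |

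The shift is either zero or downward. Over this range it is small next to the sampling uncertainty of 3 in 50 (1.3% to 16.5%).

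**The case against.** **The restriction follows from the question.** The objectives in Protocol 2.1 concern performance with the CI532, and a subject who leaves surgery with another device has no CI532 score. This stands. A reader might infer that the primary analysis is wrong or should be replaced by one that imputes scores for converted subjects. The documents do not support that: such subjects receive a different implant, and an assumed score for them answers neither objective.

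**The data are probably captured.** The questionnaire in 7.4.1 covers each implanted subject, which on its wording includes those given an alternative device, and the withdrawal form records reasons. This also stands and confines the point to planned reporting. A reader might note that the list in 9.2 does not name conversion. But that list is introduced by "Possible reasons for study discontinuation include the following" and the form itself is not shown, so no defect in the form can be claimed.

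**No event-rate analysis is defined.** Protocol 10.1 names a population for safety evaluation, and 8.1 says only that events are kept by type. Dilution therefore needs two things: rates computed on that population, and consented subjects who are not operated on. This stands, so the denominator point is conditional. The all-consented set also has the merit of keeping converted subjects in view for safety.

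**Events around a conversion are covered.** Protocol 8.1 requires a form for any event during the study, which takes in the attempted insertion. A reader might infer that converted subjects' events will be lost. The documents show only that collection after discontinuation is not described, and this is so for any discontinued subject. It is a point to clarify, not a demonstrated loss.

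None of this supplies the missing count. The completers' result still stands without the number of attempts behind it.

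**Conclusion.** The point holds as a gap in planned reporting, and the plan should be changed. Subjects converted because of difficulties with the study device leave the primary comparison, and neither 10.1 nor the SAP plans to say how many there were. The primary comparison remains suitable for CI532 performance, but it describes successful implantations only and should be read with the conversion count beside it. The size of this selection cannot be derived from the documents.

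The denominator point is secondary and conditional. Its direction is certain if any consented subject is not operated on, and its size is the factor operated/consented. It would be too strong to say that the plan will understate event rates: there is no dilution if every consented subject reaches surgery.

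The surgical rule on using an alternative device is not questioned.

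**What to change.** In Protocol 10.1 and the SAP:

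1. Report the number of attempted CI532 implantations and the number and proportion converted to another device, with an exact 95% CI, beside the primary result. Define an attempt so that sites count it alike.
2. Use subjects with an attempted CI532 implantation as the denominator for procedure- and device-related event rates. Keep the all-consented listing so that no consented subject disappears from safety.

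It would also help to state what adverse event information, if any, is collected after a converted subject is discontinued.

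The cost is one extra table, a few sentences of text and possibly slightly higher stated event rates. The primary analysis and the sample size do not change. The SAP is dated 2018 and written partly in the past tense, but both items can still be produced from records the protocol already requires, so far as these identify conversions.
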